## 14.10.2 Serious Adverse Events

An SAE is any untoward medical occurrence or effect that, at any dose,

- Results in death.
- Is life-threatening (an AE is life-threatening if the subject was at immediate risk of death from the event as it occurred, i.e., it does not include a reaction that might have caused death had it occurred in a more serious form).
- Requires or prolongs inpatient hospitalization. (Complications during hospitalization are AEs and SAEs if they prolong the hospitalization. Inpatient hospitalization is considered to have occurred if the subject has had to stay for a night at the hospital. The criterion for prolongation of hospitalization is also defined as an extra night at the hospital. Hospitalization may not constitute sufficient grounds to be an SAE if it is solely for diagnostic tests [even if related to an AE], elective hospitalization for an intervention already planned before subject enrollment in the clinical study, admission to a day care facility, social admission [e.g., if the subject has no place to sleep], or administrative admission [e.g., for a yearly examination]. The details of such hospitalizations must be recorded on the medical history or physical examination eCRF.)
- Results in persistent or significant disability/incapacity. (An AE is incapacitating or disabling if
  it results in a substantial and/or permanent disruption of the ability to carry out normal life
  functions.)
- Results in a congenital anomaly/birth defect.
- An important medical event that may not result in death, be life-threatening, or require hospitalization, may be considered an SAE when, based upon medical judgment, the event may jeopardize the safety of the subject, and may require medical or surgical intervention to prevent 1 of the outcomes listed above in this definition. Examples of such events are intensive treatment in an emergency room or at home for allergic bronchospasm, blood dyscrasia, or convulsions that do not result in hospitalization.

# 14.10.3 Serious Adverse Event Reporting

For any SAE during the clinical study, whether or not related to the study drug and/or procedure, the investigator must:

- 1. Take prompt medical action, if necessary. The safety of the subject is the first priority.
- 2. Ensure that the event is evaluated as an SAE. Immediately notify (within 24 hours of receipt of the event) the fax number on the SAE form.

The demographics, medical history, drugs/therapies, and medical and surgical procedures forms must also be available for review in the eCRF.

4. Send any relevant information or anonymized medical records (e.g., laboratory test results) to the CC , within 24 hours of receipt of this relevant information.

П

- 5. Monitor and record the progress of the event until it resolves or reaches a stable condition, with or without sequelae. For all additional follow-up evaluations, complete an updated SAE report within 24 hours of receipt of the updated information.
- 6. Obtain and maintain in the subject files all pertinent medical records, information, and medical judgments from colleagues who participate in the treatment and follow- up of the subject. If necessary, contact the subject's personal physician or hospital staff to obtain further details.
- 7. When the outcome of the event is known, complete an updated SAE report, if appropriate.
- 8. Prompt notification of SAEs by the investigator is essential so legal obligations and ethical responsibilities toward the safety of subjects are met. The Sponsor must notify both the local regulatory authority and other regulatory agencies about the safety of a product under clinical investigation. The Sponsor or its delegate (i.e., the CRO) will comply with country-specific regulatory requirements relating to safety reporting to regulatory authorities, Institutional Review Board (IRB)/Independent Ethics Committee (IEC) and investigators. Investigator safety reports are prepared for suspected unexpected serious adverse reactions (SUSARs) according to local regulatory requirements and are forwarded to investigators as necessary.

An investigator who receives an investigator safety report describing an SAE(s) or other specific safety information (e.g., summary or listing of SAEs) from the Sponsor or its delegate (i.e., the CRO) will file it (i.e., within the Trial Master File), and will notify the IRB/IEC, if appropriate according to local requirements.

9. Comply with the applicable regulatory requirement(s) related to the reporting of SAEs to the IRB/IEC.

## 14.10.4 Procedure for Reporting an Adverse Event of Special Interest

For any AESI during the clinical study, whether or not related to the treatment, the investigator must:

1. Take prompt medical action, if necessary. The safety of subjects is the first priority.

2. Ensure that the event is evaluated as an AESI. Notify (within 3 days of receipt of the event) of an AESI report, by email or fax. Refer to Section 14.10.1.

CCI

The demographics, medical history, drugs/therapies, and medical and surgical procedures forms must also be available for review in eCRF.

- 3. Send any relevant information or medical records (e.g., laboratory test results) to within 3 days of receipt of this relevant information.
- 4. Monitor and record the progress of the event until it resolves or reaches a stable condition, with or without sequelae. For all additional follow-up evaluations, update the AESI form within 3 days of receipt of the updated information.
- 5. Obtain and maintain in the files all pertinent medical records, information, and medical judgments from colleagues who participate in the treatment and follow-up of the subject. If necessary, contact the subject's personal physician or hospital staff to obtain further details.
- 6. When the outcome of the event is known, update the AESI form, if appropriate.

# 14.10.5 Procedure for Reporting Pregnancies

Any pregnancy during clinical studies where the fetus could have been exposed to the study drug must be monitored until its outcome to ensure the complete collection of safety data. If a subject becomes pregnant, the investigator must:

- 1. Withdraw the subject from the clinical study. The subject must receive no further injection of the study drug.
- 2. Complete fully the Pregnancy Surveillance Form Part I: History and Start of Pregnancy. Send by email or fax along with the exit form within 24 hours of receipt of the information, to Refer to Section 14.10.5.

Note: Immediate pregnancy reporting is required by the investigator if it occurs during the clinical study or within 12 weeks ( $\pm$  5 days) of receiving the last dose of study drug, whether or not the event is considered related to the investigational product.

- 3. Monitor and record the progress of the pregnancy until its outcome. Contact the subject's regular physician (general practitioner or gynecologist) or hospital staff to obtain further details and ask for regular follow-up information.
- 4. Provide tri-monthly updates until the final outcome of the pregnancy, by completing the Pregnancy Surveillance Form Part II: Course and Outcome of Pregnancy. For all additional This document is confidential.

- follow-up evaluations, send the form by email or fax within 24 hours of receipt of the information. If the subject can no longer be reached (i.e., lost to follow-up), documentation of the non-response/contact with 2 phone calls and a letter (certified with return receipt) is required.
- 5. At the outcome of the pregnancy, complete fully the Pregnancy Surveillance Form Part II: Course and Outcome of Pregnancy. Print and send the form by email or fax to within 24 hours of receipt of the information.
- 6. If the pregnancy leads to an abortion (i.e., voluntary abortion, spontaneous abortion, or therapeutic abortion), in utero death or congenital anomaly, follow the procedure for declaration of/reporting an SAE (see Section 14.10.3).

## 14.10.6 **Suspected Unexpected Serious Adverse Reactions**

AEs that meet these criteria will be classified as SUSARs and reported to the appropriate regulatory authorities under applicable regulatory requirements for expedited reporting:

- Serious
- Unexpected (i.e., the event contradicts the Reference Safety Information in the IB for nemolizumab)
- There is at least a reasonable possibility there is a causal relationship between the event and the study treatment

The Sponsor or its delegate will comply with country-specific regulatory requirements relating to safety reporting to regulatory authorities, IRB/IEC and investigators. Investigator safety reports are prepared for SUSARs according to local regulatory requirements and Sponsor policy and are forwarded to investigators as necessary.

An investigator who receives an investigator safety report describing a SUSAR or other specific safety information (e.g., summary or listing of SAEs) from the Sponsor or its delegate will file it (i.e., within the Trial Master File), and will notify the IRB/IEC, if appropriate according to local requirements.

#### 14.10.7 **Overdose**

Study drug overdose is the accidental or intentional use of the drug in an amount higher than the dose being studied. The investigator must immediately notify the Sponsor of any occurrence of overdose with study drug (see Section 14.10).

## PHARMACOKINETIC ANALYSIS

#### 16 PHARMACOKINETIC PARAMETERS

PK parameters will be calculated by a dedicated CRO with a non-compartmental analysis (NCA) using actual sampling times. For PK calculations, the program package Phoenix WinNonlin (Version 8.1 or above) will be used. Phoenix WinNonlin will also be used to generate concentration-time plots. Details related to the calculation of PK parameters will be described in a PK plan, which will be finalized before the beginning of PK analysis.

The following PK parameters will be calculated:

Primary PK parameters

Observed maximum serum concentration  $C_{max}$ 

AUC0-inf Area under the concentration-time curve extrapolated to infinity, calculated, if

feasible, as  $AUC_{0-last} + C_{last}/\lambda_z$ , where  $C_{last}$  is the last measurable drug concentration

Secondary PK parameters

Area under the concentration-time curve over the specified interval, calculated with AUC0-4 weeks

the linear trapezoidal method

Area under the concentration-time curve from administration to the last observed  $AUC_{0-last}$ 

concentration time t, calculated with the linear trapezoidal method

Time to achieve Cmax  $T_{max}$ 

Half-life, calculated, if feasible, as  $\ln 2/\lambda_z$  $t_{1/2}$ 

Total body clearance for extravascular administration, calculated, if feasible, as Cl/F

dose/AUC0-inf

Vd/F Apparent volume of distribution for extravascular administration, calculated, if

feasible, as dose/AUC0-inf •  $\lambda_z$ 

For parameters requiring the terminal elimination rate constant  $\lambda_z$  to be estimated, it will be calculated, if feasible, by log-linear regression using at least 3 concentration-time points excluding  $C_{\text{max}}$ .

All individual concentration data and PK parameters will be listed for AI and DCS together with summary statistics of geometric mean, median, arithmetic mean, standard deviation, CV, and minimum and maximum. Plots will be provided in original scale and semi-logarithmic scale for each subject in addition to mean data plots.

## 16.1 **Exposure-Response Analysis**

If the confidence intervals (CIs) for the primary PK parameters are outside the 80.00 to 125.00% acceptance range, acceptance of greater differences in PK parameters might be supported based on a clinical justification that these differences are clinically irrelevant PK/pharmacodynamic (PD) models may support lack of clinically meaningful impact on AD (peak pruritus numeric rating scale [PP NRS], Eczema Area and Severity Index, and Investigator's Global Assessment) or PN (PP NRS) clinical endpoints. This approach is based on the observation that, within the considered magnitude of dose changes, relationship between dose and average exposure is linear. Details related to exposure-response analysis will be described in a PK plan, which will be finalized before the beginning of PK analysis.

## 17 STATISTICAL ANALYSIS

A statistical analysis plan will be prepared after the protocol is approved. This document will explain the definition of analysis variables and analysis methodology to address all study objectives. The statistical analysis plan will serve as a compliment to the protocol and supersedes it if differences occur.

The statistical evaluation will be performed using SAS® software version 9.4 or higher (SAS Institute, Cary, NC). All data will be listed. All primary and secondary efficacy endpoints, and safety endpoints will be summarized. Summary statistics will be presented by treatment group. For continuous variables, data will be summarized with the number of subjects (N), mean, standard deviation, median, minimum, and maximum by treatment group. For categorical variables, data will be tabulated with the number and proportion of subjects for each category by treatment group.

# 17.1 Determination of Sample Size

From previous studies conducted with nemolizumab, inter-subject standard deviation is expected to be approximately 38.5%, which provides an inter-subject variability CV for the primary PK parameters of 40%. A sample size of 96 subjects per arm (AI or DCS) should provide a 90% power of claiming the bioequivalence between AI and DCS administration within the range 80.00 to 125.00% for the primary PK parameters with the expected GMR of 0.95.

Approximately 192 healthy subjects are planned to be randomized in this study.

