Only adult subjects will be enrolled in this study as no significant impact of age was evidenced for the nemolizumab PK profile.

A total of 21 blood samples will be collected, i.e., 1 before and 20 after nemolizumab administration (i.e., pre-dose, 12 hours, 24 hours, 3, 4, 5, 6, 7, 8, 9, 10, 11, 15, 22, 29, 36, 43, 50, 57, 71, and 85 days post-dose). PK blood sampling will be performed over a 12-week period after nemolizumab administration to enable a reliable estimation of nemolizumab total systemic exposure for both the AI and DCS. The sampling schedule includes frequent sampling around the expected time to maximum concentration ( $T_{max}$  [5–9 days]).

A sample size of 192 subjects, i.e., 96 subjects per arm (AI or DCS), should provide a 90% power of claiming the bioequivalence between AI and DCS administration within the range of 80.00 to 125.00% for the primary PK parameters with the expected GMR of 0.95. This study adopts a conservative approach by requiring the standard bioequivalence range of 80.00 to 125.00% to be met for the primary PK parameters (AUC $_{0-inf}$ , , and  $C_{max}$ ) of nemolizumab.

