### 10.4 Study Withdrawal, Removal, and Replacement of Subjects

Although the importance of completing the entire study will be explained to the subjects, any subject may discontinue his/her participation in the study at any time and for whatever reason, specified or unspecified, and with no prejudice. No constraints are to be imposed on the subject, and when appropriate, a subject may be treated with other conventional therapy when clinically indicated. Investigators or the Sponsor can also withdraw subjects from the study if deemed necessary.

Reasons for discontinuing the study include:

- Withdrawal by subject
- Protocol violation

Examples

- Non-compliance with the study schedule
- Use of prescription medications, except to treat AEs and contraception.
- Lost to follow-up
- **AEs** 
  - Occurrence of AEs, including laboratory abnormalities, not compatible with the continuation of subject participation in the study, in the investigator's opinion, or unacceptable to the subject to continue, including but not limited to:
    - Serious immediate-type allergic manifestations, including anaphylactic reaction
    - Diagnosis of a malignancy (except curatively treated in situ cervical carcinoma, squamous cell carcinoma [Bowen's disease] or basal cell carcinoma)
    - Opportunistic infections such as but not limited to active TB and other infections whose nature or course suggest an immune-compromised or immune-suppressed status
    - Any serious infection or any severe infection requiring treatment with parenteral antibiotics or oral antibiotics/antivirals/antifungals for > 2 weeks considered related to study drug administration
    - Confirmed or suspected COVID-19 (temporarily, see Section 10.4.2)
- Pregnancy (see Section 10.4.1)
- Physician decision

- Sponsor request
- Study terminated by Sponsor
- Other

The reason(s) for withdrawal will be documented in the electronic case report form (eCRF). Subjects who have been enrolled and treated will not be replaced by another subject.

When a subject discontinues the study, he/she will be assessed and followed according to the guidelines in Section 12.2.1 (Early Termination Visit).

Reasonable efforts will be made to contact subjects who are lost to follow-up. These efforts must be documented in the subject's file.

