## 17.2 Analysis Populations

**Safety Population:** The safety population (SAF) will consist of all randomized subjects who received the single dose of study drug and will be the primary population for all safety data.

**Pharmacokinetic Population:** The PK population will include all randomized subjects who received the dose of study drug and provided evaluable data that can be used for the PK analyses. The PK population will be the primary population for PK analyses.

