# 17.3 Statistical Analysis of Pharmacokinetic Parameters

# 17.3.1 Primary Pharmacokinetic Endpoints

For the primary PK endpoint analyses, a linear mixed-effect model will assess the log transformed PK parameters (AUC $_{0\text{-inf}}$  and  $C_{max}$ ) of nemolizumab, with treatment (administration with AI or DCS) and injection site as fixed effects and subject as a random effect. Some clinically important baseline characteristics may also be included in the model. The AUC and  $C_{max}$  GMR between treatments (nemolizumab administered with AI [test] or DCS [reference]) after backtransformation and the corresponding 90% CI will be provided overall.

Acceptance criterion for bioequivalence is a 90% CI for the test/reference ratio of the geometric means of the parameters under consideration within the 80.00 to 125.00% range.

In addition, the GMR and 90% CI will be provided by injection site for information only.

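### Does the 90% power in Protocol 17.1 have to be the chance that Cmax and AUC0-inf both pass?

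*Protocol*

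**What the plan says.** Section 17.1 states the claim, which the synopsis and section 9.2 repeat: "A sample size of 96 subjects per arm (AI or DCS) should provide a 90% power of claiming the bioequivalence between AI and DCS". The limits are 80.00 to 125.00%, and the claim covers the primary parameters without separating them. Section 17.1 gives a between-subject SD of about 38.5%, a CV of 40% and an expected GMR of 0.95, each once and for both parameters. It plans about 192 randomized subjects and gives no correlation and no dropout rate.

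The success rule is in section 9.2, which describes the approach as "requiring the standard bioequivalence range of 80.00 to 125.00% to be met for the primary PK parameters" and names AUC0-inf and Cmax. Section 17.3.1 sets the test: "Acceptance criterion for bioequivalence is a 90% CI for the test/reference ratio of the geometric means of the parameters under consideration" lying within the same range.

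Three other places bear on how many subjects contribute:

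- Section 17.2 defines who is analysed: "The PK population will include all randomized subjects who received the dose of study drug and provided evaluable data that can be used".
- Section 16: the terminal rate constant behind AUC0-inf is "calculated, if feasible, by log-linear regression using at least 3 concentration-time points".
- Section 10.4: "Subjects who have been enrolled and treated will not be replaced by another subject".

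**The concern.** When two parameters must both pass, the chance of success cannot exceed the chance for either one, and it is lower unless they rise and fall together almost perfectly. A reader may take 90% as the probability that the bridging criterion is met. That reading would be too optimistic for many plausible correlations, and more so if some subjects yield no AUC0-inf.

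The text does not say which probability is meant, nor whether 96 is the number randomized or the number evaluable. At stake is the planning probability only. Requiring both parameters to pass does not raise the false-positive rate, so no adjustment of the 90% confidence intervals would follow in either case.

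**Working it through.** **Inputs.** From section 17.1: log-scale SD 0.385, GMR 0.95, n = 96 per arm. From section 17.3.1: limits 0.80 and 1.25 with a 90% CI, which is two one-sided tests at 0.05 each. From section 11.3.1: 1:1 allocation.

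**SD and CV.** √ln(1 + 0.40²) = 0.3853, so the SD of 38.5% and the CV of 40% agree.

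**Power for one parameter, n = 96.**

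- SE = 0.385 × √(2/96) = 0.0556.
- Distance from ln 0.95 = −0.0513 to the lower limit ln 0.80 = −0.2231 is 0.1718, or 3.09 SE. Distance to the upper limit ln 1.25 = 0.2231 is 0.2744, or 4.94 SE.
- The t quantile on 190 degrees of freedom is 1.653. Power ≈ Φ(3.09 − 1.653) − Φ(−(4.94 − 1.653)) ≈ 0.925 − 0.0005 ≈ 0.924.
- Integrating over the sampling distribution of the variance gives 0.9241. Using two fewer degrees of freedom for injection site leaves it at 0.924.

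**Smallest n for 90% per parameter.** The same calculation gives 0.8999 at 87 per arm and 0.9029 at 88. So 96 exceeds the need by 8 per arm, and 8/96 = 8.3% can be lost before per-parameter power falls below 90%. If 0.40 were used as the log SD itself, 96 per arm would give 90.6% and 94 would suffice.

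**Power for both parameters.** This needs a correlation between the log parameters, which the protocol does not give. Simulated bivariate estimates, with the same SD and GMR for both parameters, give:

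| Assumed correlation | 96 per arm | 91 per arm (5% loss) | 86 per arm (10% loss) |
|---|---|---|---|
| 0 | 85.4% | – | – |
| 0.5 | 87.0% | 85.0% | 82.7% |
| 0.8 | 88.8% | 87.1% | 85.1% |
| 0.9 | 89.8% | 88.2% | 86.4% |
| 0.95 | 90.6% | 89.1% | 87.4% |
| 1 | 92.4% | – | – |

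At independence this is the square of the single figure, 0.924² = 0.854. At 96 per arm the joint power crosses 90% at a correlation between 0.91 and 0.92. If only AUC0-inf loses subjects and Cmax stays on 96, joint power for correlations 0.5 to 0.95 is about 86 to 89% with 91 subjects per arm for AUC0-inf, and 85 to 88% with 86.

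**Variance explained by the model.** Section 17.3.1 fits injection site and allows baseline characteristics. If these explained 10% of the log variance, the residual SD would be 0.385 × √0.9 = 0.365. Joint power at 96 per arm would then be 90.4% at correlation 0.5 and 91.8% at 0.8.

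**The case for a change.** The strongest case for a change is that the sentence speaks of claiming bioequivalence, and under section 9.2 that claim needs both parameters. Read literally, 90% then holds only above a correlation of about 0.91 with no loss. The figure stands in the protocol itself, so a later analysis plan does not excuse it. AUC0-inf is computed only where feasible and treated subjects are not replaced, so some loss is realistic; with 5% loss in both parameters, joint power stays below 90% at every correlation from 0.5 to 0.95. The provision in section 16.1 for clinical justification outside the range is a fallback and does not redefine the event being powered.

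The label is indeed missing, and joint power probably lies a little under 90%. It does not follow that the stated figure is wrong. One SD, one CV and one GMR without a correlation are what a single-parameter calculation uses, and on that reading the sentence is true and cautious. Since 2 × 96 = 192 are to be randomized, 96 is the randomized number, and the 8.3% cushion covers moderate loss for each parameter. The lower joint figures need assumptions the protocol does not make: a loss rate, no variance explained by the model, and a GMR of 0.95 for both parameters at once.

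**Conclusion.** No change follows. The 90% is met for each primary parameter on the protocol's own inputs (92.4% at 96 per arm, 90% at 88). Joint power is 85.4 to 90.6% for assumed correlations of 0 to 0.95 without loss. The gap to 90% is about 1 point at 0.8, larger with loss, and absent if the model explains about 10% of the log variance. Correlation, loss and explained variance are all assumptions here.

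Anyone who needs the joint probability can compute it from the stated inputs under a correlation of their own choosing. The sample size, the PK population, the model and the both-must-pass rule remain sound as written, and the trial's conclusion will rest on the observed confidence intervals, which no labelling of the planning power can alter.
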